# Plan for treatment assignment and randomization

Aims 1 and 2 of the study do not involve allocation to treatment groups.

Aim 3 is a randomized placebo-controlled double-blinded intervention study to examine the effect of metformin versus matching placebo on pulmonary vascular function. We anticipate enrolling 75 participants studied in Aims 1 and 2 who display abnormal pulmonary vascular hemodynamics into Aim 3. Participants with contraindications to metformin will be excluded as outlined in Table 1.

In order to allocate evenly, without bias, and in a manner blinded to both participants and investigators, we will randomize participants to treatment group (metformin versus placebo) with the assistance of the investigational drug pharmacy. Randomization will be performed in a 1:1 fashion in groups of 4 to assure balanced study groups, and will be stratified by type of pulmonary vascular dysfunction (resting or exercise-induced).

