Metformin or placebo administration: The participant will then receive, at random, either metformin or placebo in a 1:1 blinded fashion. Randomization will be stratified by type of PH (resting vs exercise-induced) and will be performed in blocks of 4 to assure balanced group sizes. Because we wish to ensure equal gender representation into the treatment and placebo groups, randomization will be done separately for men and women. Participants will be given 500mg capsules of metformin or matching placebo and instructed to take 500mg twice daily for 1 week, followed by 1g twice daily for a total of 3 months. Participants may receive study medication by mail or at study visits. We will exclude individuals with contraindications to metformin use as outlined in the exclusion criteria, and participants will be monitored for clinical symptoms of lactic acidosis and hypoglycemia. Medication compliance will be assessed with pill counts. The proposed use of metformin is IND-exempt.

Visit 3 (Interim): The third study visit will take place at MGH or remotely, approximately 2-4 weeks after initiation of metformin or placebo. An interim medical history will be taken by study staff in person or by telephone to assure that no contraindications to study participation or potential side effects have developed. Seated blood pressure and pulse may be obtained, and weight may be measured. Fasting blood work will be obtained at MGH or a local lab. We may collect up to 100 ml of blood for these measurements and storage of samples for future use.

Visit 4 (Interim): The fourth study visit will take place approximately 7-12 weeks after initiation of metformin or placebo. An interim medical history will be taken to assure that no contraindications to study participation or potential side effects have developed. Seated blood pressure, pulse, and anthropometrics will be obtained. Fasting blood work will be obtained. We will collect up to 100 ml of blood for these measurements and storage of samples for future use. Participants will undergo venous endothelial cell collection as outlined previously, as well as an electrocardiogram (ECG).

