Statistical analyses for Aim 3: We will compare the change in  $\Delta mPAP/\Delta CO$  slope in the metformin vs placebo groups. The "delta" in slope will be defined as the 3-month minus the baseline value. We will apply a two-sample t-test to compare the delta in the two groups in an unadjusted intention-to-treat analysis. An adjusted analysis will be performed using a multivariable random effects linear regression model adjusted for baseline  $\Delta mPAP/\Delta CO$ , such that [delta  $\Delta mPAP/\Delta CO$ ] = intercept +  $\beta_1$ \*treatment group +  $\beta_2$ \* $\Delta mPAP/\Delta CO_{baseline}$ , with treatment group and  $\Delta mPAP/\Delta CO_{baseline}$  as fixed effects and treatment group modeled as a random effect. Given that the randomization will be stratified by type of pulmonary vascular dysfunction (resting versus exercise-induced), we will use a 'strata' statement to indicate PH type in the model. We anticipate that metformin will improve PAEC insulin resistance (% change in the ratio of p-eNOS to total eNOS) and also pulmonary hemodynamics. In secondary analyses, we will examine the correlation between PAEC and venous endothelial cell insulin resistance among treatment groups.

Statistical power for Aim 3: We will power the study for the between-group comparison (metformin vs placebo) of the delta in  $\Delta$ mPAP/ $\Delta$ CO (3 month – baseline). In 15 prior patients with repeat testing within 12 weeks, the reproducibility of  $\Delta$ mPAP/ $\Delta$ CO was robust, with an intra-individual CV of 0.92, and a standard deviation (SD) of the delta (12-week minus baseline) of 0.46. We will assume a similar SD in this study. In our experience with intervention studies, attrition from non-compliance is ~15%. With a target enrollment of 75 participants and 15% loss to follow-up, we would have 64 participants completing the study. In preliminary studies, the difference in  $\Delta$ mPAP/ $\Delta$ CO slope among diabetics and non-diabetics was 0.7mmHg/L. We estimate >80% power to detect up to 50% of the difference in  $\Delta$ mPAP/ $\Delta$ CO between diabetics vs nondiabetics (0.35mmHg/L) among the treatment groups using a two-sided t-test with 5% type I error.

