Cardiometabolic Disease and Pulmonary Hypertension

NCT03349775

Document Version 1/15/2021

Statistical Analysis Plan

For METCPET clinical trial interim analysis

Distributions and outliers of continuous variables will be examined using histograms and Whisker box plots. Variables with skewed distribution will be natural log-transformed to approximate normal distribution. Outliers detected by box plots will be examined case-by-case to ensure no data input errors. Categorical variables (race and ethnicity) will be checked manually in all subjects (n=15). Covariate data including age, sex, race/ethnicity, height in inches, weight in pounds, Body Mass Index (BMI), heart rate, systolic blood pressure, diastolic blood pressure will be summarized and reported in mean (Standard Deviation) for continuous variables and frequencies (percentage) for categorical variables. Between-group differences will be compared using two independent samples t-test or Fisher's exact test as appropriate.

We will calculate PAP/CO slope by using serial pulmonary artery pressure (PAP) and cardiac output (CO) measurements before and after Metformin treatment for each randomized subject. Change in PAP/CO slope will then be generated by subtracting pre-treatment PAP/CO from post-treatment PAP/CO. The primary analysis will be between-group comparisons in PAP/CO slope change pre- and post-treatment in an intention-to-treat analysis using Welch's t-test or Two independent samples t-test depending on the variances in both groups. We will also conduct secondary analysis on other hemodynamic and gas exchange variables with the same procedures. Mean change differences between groups will be reported with 95% confidence interval, and between-group PAP/CO slope changes and mean PAP changes will be visualized using Whisker box plots. P values are two-sided with a significance level of 0.05. All statistical analyses will be performed in SAS 9.4 (Cary, NC).

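### The adjusted Aim 3 model enters treatment group as both a fixed and a random effect, so under REML the data cannot determine its standard error or p-value

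*Protocol*

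**What the plan says.** Protocol section 6, under the statistical analyses for Aim 3, first sets out an unadjusted intention-to-treat t-test. The outcome is a single number per participant: the delta "in slope will be defined as the 3-month minus the baseline value".

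It then continues: "An adjusted analysis will be performed using a multivariable random effects linear regression model adjusted for baseline" slope. The displayed equation has an intercept, a treatment coefficient and a baseline-slope coefficient, and no random term. The clause that follows lists treatment and baseline slope "as fixed effects and treatment group modeled as a random effect". For the randomization stratum it adds that "we will use a 'strata' statement to indicate PH type in the model".

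On the design, section 4 (plan for treatment assignment and randomization) states: "Randomization will be performed in a 1:1 fashion in groups of 4 to assure balanced study groups". It says that the allocation "will be stratified by type of pulmonary vascular dysfunction (resting or exercise-induced"). Section 5 (metformin or placebo administration) repeats the PH-type stratification and adds that "randomization will be done separately for men and women".

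The SAP, which covers the interim analysis, has no adjusted model: "The primary analysis will be between-group comparisons in PAP/CO slope change pre- and post-treatment in an intention-to-treat analysis", by Welch or pooled t-test. It names SAS 9.4. Neither document says whether a mixed model would be fitted by ML or REML.

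**The concern.** A random effect needs a grouping factor whose levels vary beyond what the fixed effects explain. Here the only grouping factor named is the treatment itself. It has two levels, and the fixed intercept and treatment terms already fit both. With one delta per participant and no site, subject or other cluster, no variation remains from which to estimate the random variance.

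This is the only treatment comparison in the documents that adjusts for baseline slope and PH type. Fitted by REML as written, its standard error, confidence interval and p-value would depend on where the optimizer starts or stops. The adjusted result could then disagree with the t-test for no reason in the data.

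**Working it through.** **Inputs.** From Protocol section 6 (statistical power for Aim 3): SD of the delta 0.46, difference 0.35, two-sided 5%, 75 enrolled with 15% loss. 75 × 0.85 = 63.75, which the protocol rounds to 64; I take this as 32 per arm.

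**The plan's own figure.** The t-test standard error is 0.46 × √(1/32 + 1/32) = 0.115, and 0.35/0.115 = 3.04. Power from the noncentral t with 62 df is 85.0%, so the stated figure of more than 80% reproduces. It does not involve the adjusted model.

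**Why REML cannot estimate the random variance.** Write V = σ²I + σg²ZZ′, where Z holds the two arm indicators and X holds intercept, treatment and baseline slope.

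1. The columns of Z are (intercept − treatment) and (treatment), so they lie in the span of X.
2. REML uses only contrasts K′y with K′X = 0. Then K′Z = 0 and K′VK = σ²K′K. σg² has vanished from the likelihood.
3. The estimate b1 equals the ordinary least-squares estimate for every σg².
4. Each arm effect enters b1 with coefficient −1 (placebo) or +1 (metformin). Hence Var(b1) = ANCOVA variance + 2σg².

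So the data say nothing about σg², but the reported standard error depends on it directly.

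**Size with the planning figures.** Var(b1) = 0.46² × (2/32) + 2σg² = 0.013225 + 2σg², referred to t with 62 df. For simplicity this takes 0.46 as the residual SD, with no gain from baseline adjustment.

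| σg² | SE of b1 | t | p |
|---|---|---|---|
| 0 | 0.115 | 3.04 | 0.003 |
| 0.005 | 0.152 | 2.30 | 0.025 |
| 0.01 | 0.182 | 1.92 | 0.059 |
| 0.05 | 0.337 | 1.04 | 0.30 |

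The planned effect loses significance at σg² = [(0.35/2.00)² − 0.013225]/2 = 0.0087, which is 4% of the residual variance 0.46² = 0.2116.

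**Numerical check of the flatness.** One simulated data set had 32 per arm, SD 0.46, true effect −0.35, and an assumed baseline slope of mean 3 and SD 1.3. The REML log-likelihood was −38.295530 at random-effect SDs of 0, 0.05, 0.1, 0.2, 0.35, 0.46, 1 and 3. b1 stayed at −0.343 while its standard error ran from 0.113 to 4.244. With PH type added as a fixed effect the likelihood was again flat (−38.151315). The ML log-likelihood fell steadily from −38.68 at zero to −45.92 at 3, so ML returns zero.

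**Illustrative fits in statsmodels.** A second data set was built to have an effect of exactly −0.35 and residual SD 0.46.

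| Fit | σg² | SE of b1 | p |
|---|---|---|---|
| ANCOVA | none | 0.115 | 0.0035 |
| REML: BFGS, L-BFGS or CG | 0.2116 | 0.66 | 0.60 |
| REML: Powell | 1.72 | 1.86 | 0.85 |
| ML | about 0 | 0.113 | 0.002 |

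The REML fits in the table all have the same log-likelihood, −44.93768. A further REML fit, by Nelder-Mead, stopped at variance 0.233 with a standard error of 0.009. That is below the minimum the formula allows, so it is a numerical failure. SAS 9.4 was not available, and its behaviour was not tested.

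**The case against.** The case for leaving this alone, or rating it minor, has several parts.

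- **The consequence depends on REML, which neither document names.** True. Under ML the fit falls back to ANCOVA, and the displayed equation is itself ANCOVA. An analyst who follows the equation and ignores the clause gets a sound model. But the clause is part of the specification, and a prespecified p-value should not hang on an unstated estimator.
- **The software fits are artefacts.** Largely true. The REML variance of 0.2116 equals the residual variance because the optimizer never left its default start: other starts gave 0.0002, 0.002, 0.021 and 0.63. Four of the five REML fits also warned of a non-positive-definite Hessian, so the problem would usually be visible. The fits only illustrate; the flatness is algebraic and holds for any data set.
- **The variances in the size table are arbitrary.** True, and the data favour none of them. That is the defect itself. The extra term can only widen the standard error, so by the formula it cannot create a false positive for metformin.
- **Treatment-by-stratum cells may have been meant.** On that reading REML is not flat (−38.30 at zero to −44.46 at an SD of 3). The text does not say so, although its next sentence brings in PH type. If a random coefficient on the treatment indicator was meant, the likelihood is just as flat, and σg² rather than 2σg² is added.
- **Sex and the strata statement go beyond the double listing.** Fair. Deleting the clause cures the defect. The covariates complete the model because the randomization uses them.

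**Conclusion.** The concern holds. As written, the adjusted model enters the same two-level factor twice. Under REML, one of the two standard estimators, its standard error, confidence interval and p-value are undetermined. At the planning values the result can lie anywhere from p = 0.003 to clearly non-significant, with an identical likelihood and an identical point estimate.

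The damage is limited to the adjusted comparison. The treatment estimate, the unadjusted t-test, the SAP's primary interim analysis and the power statement are unaffected. It should be corrected before the final analysis, but it does not threaten the main comparison.

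The figures assume 32 completers per arm and the protocol's SD of 0.46. The algebra rests on neither.

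**What to change.** Delete the clause that makes treatment group a random effect, and call the model ANCOVA. Fit the delta on treatment, baseline slope, PH type and sex, all as fixed effects, with residual error only. Entering PH type as a covariate replaces the strata statement, whose form in a linear model the protocol does not explain. Sex belongs in the model because section 5 randomizes men and women separately; section 4 does not mention this, so the two sections should be aligned.

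The cost is wording only, with no new data. PH type and sex use two more degrees of freedom than the displayed equation. With 64 completers the residual df go from 64 − 3 = 61 to 64 − 5 = 59, and the two-sided 5% critical t stays at about 2.00.

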#### 7. RISKS AND DISCOMFORTS

#### **Procedures**

Phlebotomy and IV placement: In order to minimize the risks of phlebotomy, participants will be asked about previous difficulty with phlebotomy (particularly pre-syncope or syncope) and appropriate measures will be taken, as needed. During venipuncture, the participant will be in a sitting position. At each study visit, no more than 150 cc of blood is taken, and in total over the course of the study, no more than 450 cc (2 cups) of blood will be obtained. This is within the Red Cross guidelines (less than 500 cc every 2 months). Risks of phlebotomy include anemia, and the amount of blood collected will be reduced if the investigator feels there is a significant risk of anemia. Other risks include discomfort, bleeding or bruising where the needle enters the skin, and rarely, fainting or infection may occur.

Protection against risk: The participants will be asked whether they are feeling well during the blood draw and throughout the visit. If the participant is not feeling well, the specific discomfort will be addressed, and the participant will be referred for evaluation, as needed. If a participant feels lightheaded during the venipuncture or blood draw, the procedure is suspended. The participant will be provided with orange juice and observed until the light-headedness resolves. If the participant is willing, s/he may continue the protocol once this symptom has resolved. If anemia is identified at any time during the study (Hemoglobin, Hb  $\leq$  9 g/dL), no further blood draws will be conducted until Hb is again documented as Hb  $\geq$  9 g/dL.

**6-minute walk test:** The 6-minute walk test is a simple and practical non-invasive test to evaluate functional capacity. Rarely there may be an increased risk of arrhythmias or cardiovascular collapse. However, each participant determines the level and intensity of walking during the test, and it has been performed on thousands of older persons and patients with heart failure or cardiomyopathy without serious adverse events. Rarely Participants with absolute contraindications are already excluded from the study as outlined in Table 1 (unstable angina, myocardial infarction in previous month). Relative contraindications include a resting heart rate > 120 bpm, or uncontrolled hypertension (systolic blood pressure > 180 mmHg, diastolic blood pressure > 100 mmHg).

Protection against risk: Prior to testing, heart rate and blood pressure will be obtained, and testing will be deferred if criteria are met and participants referred to their treatment team for follow-up as necessary. All study personnel administering the 6-minute walk test will be appropriately trained, and will have completed cardiopulmonary resuscitation training. Testing will be stopped immediately if the participant wishes to do so, or experiences chest pain, intolerable dyspnea, leg cramps, staggering, diaphoresis, or pale and ashen appearance. Testing will be performed at MGH hospital with medical care immediately available if necessary.

**Oral glucose tolerance test:** A drawing IV will be placed so that blood draws at three time points can be performed with minimal discomfort. Potential risks include nausea, stomach discomfort, diarrhea, and constipation.

Protection against risk: A blood glucose (BG) measurement will be checked in order to assure safety in proceeding to an oral glucose tolerance test (OGTT), and a pre-OGTT value of > 200mg/dL will preclude OGTT administration.

**Venous endothelial cell collection:** Insertion of the J wire once the IV has been placed is painless and is associated with possible bleeding or bruising associated with placement of the IV, and a potential risk of thrombophlebitis.

Protection against risk: This technique has been performed safely over 2,000 times in [name] laboratory without reported adverse effects, and MGH co-investigators have undergone formal training in her laboratory. A vast array of J-tipped wires are approved by the FDA and are used clinically for insertion of central and peripheral catheters into veins and are designed to be atraumatic. The J wire will only be inserted using sterile IV sites.

Transthoracic echocardiography: Transthoracic echocardiography will be performed according to standard medical practice, and is associated with minimal discomfort or risk to study participants. Rarely there is minor transient discomfort during echocardiography due to the pressure of the ultrasound probe against the chest or abdominal wall. In order to better visualize tricuspid Doppler signal, microbubble contrast may be used to permit more accurate determination of right heart hemodynamics (Mulvagh SL et al, American Society of Echocardiography Consensus Statement on the Clinical Applications of Ultrasonic Contrast Agents in Echocardiography, J Am Soc Echocardiogr, 2008;21:1179).

Protection against risk: If discomfort occurs, the probe will be adjusted, and the study stopped at the participant's request. Microbubble contrast agents are FDA approved for use in echocardiography. These agents are safe without medically significant risks other than rare allergic events at a rate of approximately 1 per 10,000. In order to avoid this potential risk, echo contrast administration will be contraindicated and avoided in patients with known hypersensitivity to perflutren. Echo contrast will be administered by a licensed and trained cardiac sonographer.

Invasive CPET with hemodynamic monitoring and right heart catheterization: The risks of placing a right heart catheter include bleeding and bruising at the site where the catheter is inserted and pneumothorax. Other rare complications may include ventricular arrhythmias, cardiac tamponade, air embolism, infection, and pulmonary artery rupture. Specifically in patients with pulmonary hypertension, right heart catheterization is associated with low morbidity. Of 7,218 right heart catheter procedures performed in patients with pulmonary hypertension as reviewed in one study, 1% had serious adverse events, most frequently related to venous access (hematoma, pneumothorax), and the vast majority of these complications were of mild to moderate intensity with resolution spontaneously or after appropriate intervention.  Incremental ramp CPET has been shown to be a very safe procedure. Unlike the Bruce Protocol that contains sharp increments in workload in a stepwise fashion, the CPET starts off with minimal work rate (i.e. unloaded exercise) and very gradually ramps up, providing a warm-up period for individuals performing exercise. This protocol design optimizes subject comfort and safety. 103 CPET testing rarely can precipitate coronary ischemia, arrhythmias, and/or hemodynamic instability. A recently published report on the safety of CPET examined results from over 5000 tests performed on individuals with known coronary artery disease (n=1787, 35%), heart failure (n=1289, 25%), congenital heart disease (n=688, 14%), hypertrophic cardiomyopathy (n=598, 12%), pulmonary hypertension (n=194, 4%), aortic stenosis (n=212), and previous cardiac arrest (n=60, 1%). 104 Despite the high-risk features of this population, there were no mortalities at the time of testing or during a period of 48 hours thereafter. A total of 8 adverse events (0.16% event rate) occurred, most commonly sustained ventricular tachycardia (n=6) which self-terminated without intervention in all 6 cases. There was one myocardial infarction in a post-heart transplant patient with allograft coronary artery disease. A second relevant study evaluated 2037 patients who performed 4401 CPETs in the HF-ACTION Trial (Heart Failure: A Controlled Trial investigating Outcomes of Exercise Training). 105 There were no deaths, and a rate of non-fatal major cardiovascular events of <0.5 per 1000 tests. A third relevant study

to this proposal examined the records of 38,970 patients who underwent standard maximum level exercise testing in a community clinic (mean age 54±12 years, 68% male). The main reason for referral was chest pain evaluation (59%). None of the patients died during testing, and despite 14% of the study population having detectable ischemia (n=5450). Finally, in the personal experience of the coinvestigator [name] as Director of the MGH CPET Laboratory at MGH there have been no deaths or hospital admissions related to CPET despite performing over 400 studies per year in patients who often have advanced heart and lung diseases.

Protection against risk: We are recruiting participants from two sources: (1) patients who are referred for clinically indicated RHC and CPET by other physicians. In such cases, RHC and CPET are being performed for clinical reasons regardless of our research study; (2) study volunteers that undergo rigorous screening procedures prior to RHC and CPET in order to justify testing for pure research purposes. To assure a reasonable balance in risk versus benefit ratio among the latter group, we will perform studies on individuals who have dyspnea and abnormal estimated PASP (defined as >40mmHg) based on noninvasive imaging, where testing has been deemed reasonable as outlined by expert clinical consensus. 94 Right heart catheterization procedures will be performed at the MGH cardiac catheterization laboratory by licensed and board-certified interventional cardiologists. All safety protocols in place will be followed. Prior to the procedure, we will verify that the participant is at low bleeding risk by checking a complete blood count and coagulation profile. Only individuals with INR <1.5 and platelet counts > 75,000 will be eligible for right heart catheterization (see inclusion/exclusion criteria). In addition, we will perform pregnancy testing in women of child-bearing age and exclude anybody with a positive test. After verifying informed consent, a procedure time-out will be performed. Usual sterile technique will be used, and ultrasound guidance and fluoroscopy will be used to place the pulmonary artery catheter to minimize risks of the procedure. The participant will be monitored continuously with blood pressure, heart rate, and telemetry. In order to minimize the risk to the participant during CPET testing, physician supervision will be mandated for all exercise assessments. Participants with contraindications to exercise testing will be excluded (Table 1). The laboratory will have resuscitation equipment and Advanced Cardiac Life Support-trained physicians and exercise technicians. Ratings of perceived exertion and dyspnea will be monitored during testing, as will heart rate, blood pressure, and continuous electrocardiographic tracings and test will be terminated by the test operator per standard exercise testing guidelines (i.e. a > 10mmHg fall in blood pressure, ventricular tachycardia).

**First-pass radionuclide ventriculography:** This test is performed in the CPET laboratory, and involves intravenous administration of a radionuclide tracer to label red blood cells, risks are summarized under "Radiation" in the section below.

Protection against risk: This is a radiopharmaceutical that has been approved for use in our CPET laboratory (permit #15-044), and staff have been trained in safe handling of the radionuclide tracer. Pregnant or nursing participants are excluded from our protocol. A serum pregnancy test will be checked on Study Visits 1, 2, 3, 4, and 5 in women of child-bearing potential (unless already performed for clinically-indicated purposes, in which case clinical protocols will be followed).

**Pulmonary artery endothelial cell collection:** The isolation of endothelial cells will be performed on the discarded pulmonary arterial catheter tip after completion of the right heart catheterization, therefore no additional risk beyond that of the routine right heart catheterization procedure is anticipated.

